2.2 Secondary endpoints

Secondary endpoints include:

- **Subjective functional scores:**
 - Modified Cincinnati score (continuous),
 - IKDC score (continuous),
 - Tegner Lysholm score (continuous),
 - Tegner Activity Score (ordinal/continuous).Each is measured preoperatively (baseline) and at 12 months postoperatively.
- **Demographic and perioperative characteristics:**
 - Age (years),
 - Body mass index (BMI, kg/m²),
 - Time from injury to surgery (months),
 - Length of hospitalization (days).

These are used to describe and compare the two groups at baseline.

- **Safety endpoints:** Clinical complications (infection, wound problems, thromboembolic events, range of motion restriction, graft rupture) observed during follow-up. These are summarized descriptively (frequency and percentage in each group).

3. General Statistical Principles

- All statistical tests will be **two-sided**.
- The nominal significance level is **p < 0.05**.
- For multiple pairwise comparisons of the same endpoint (e.g., sensory deficit across the three follow-up time points), **Bonferroni correction** will be applied ($\alpha_{\text{corrected}} = 0.05 / \text{number of comparisons}$).

Study Protocol Title: Impact of Platelet-Rich Fibrin on Donor Site Regeneration and Functional Recovery after ACL Reconstruction with BPTB Autograft

Version 01, 21 September 2020

- Continuous variables will be summarized as **mean, standard deviation, median and range**.
- Categorical variables will be summarized as **absolute frequencies and percentages**.
- The distribution of continuous variables will be assessed using the **Kolmogorov–Smirnov** and **Shapiro–Wilk** tests. Because most continuous variables deviate from normality or sample sizes are modest, **non-parametric tests** will be used for between- and within-group comparisons.

All analyses will be performed using **R software**, version 4.3.1 (2023-06-16).

4. Baseline Comparisons

Baseline comparability of the Vivostat and Standard groups will be assessed for:

- age, BMI, time from injury to surgery, length of hospitalization.

Since these are continuous variables, they will be compared between groups using the:

- **Wilcoxon rank-sum test** (Mann–Whitney U test).

Results will be presented as in Table 1 (mean, SD, median, range, and p-values). These analyses are descriptive and serve to document the similarity of groups at baseline in this non-randomized cohort.

5. Analysis of Subjective Functional Scores

For each subjective functional score (Modified Cincinnati, IKDC, Tegner Lysholm, Tegner Activity), the following analyses will be performed:

1. **Between-group comparison at baseline:**
 - Vivostat vs. Standard, using **Wilcoxon rank-sum test**.
2. **Between-group comparison at 12 months:**
 - Vivostat vs. Standard, using **Wilcoxon rank-sum test**.
3. **Within-group change from baseline to 12 months:**
 - For each group separately, the change over time will be tested using the **Wilcoxon signed-rank test** (paired, non-parametric).

P-values will be reported for:

- Baseline vs. 12-month comparison within each group;

Study Protocol Title: Impact of Platelet-Rich Fibrin on Donor Site Regeneration and Functional Recovery after ACL Reconstruction with BPTB Autograft

Version 01, 21 September 2020

- Between-group comparisons at baseline and at 12 months (as in Table 2).

The Tegner Activity Score will be analyzed in the same way; in the current dataset, no statistically significant change over time was observed.

6. Analysis of Sensory Deficit (Primary Endpoint)

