Study Protocol Title: Impact of Platelet-Rich Fibrin on Donor Site Regeneration and Functional Recovery after ACL Reconstruction with BPTB Autograft

Version 01, 21 September 2020

COVER PAGE

Study Protocol Title : Impact of Platelet-Rich Fibrin on Donor Site Regeneration and Functional Recovery after ACL Reconstruction with BPTB Autograft

Version/Date: Version 01, 21 September 2020

NCT number: Not Available

Statistical Analysis Plan (SAP)

Study title: Sensory deficit following anterior cruciate ligament reconstruction with bone patellar-tendon bone autograft: platelet-rich fibrin (PRF) could provide a solution

Design: Single-center prospective cohort pilot study with two parallel groups (PRF / Vivostat group vs. Standard group) and repeated follow-up measurements

Sample size: 53 male patients (Vivostat n = 24; Standard n = 29)

Primary endpoint: Sensory deficit at the donor site over time (4, 8 and 12 months)

Secondary endpoints: Subjective knee function scores (Modified Cincinnati, IKDC, Tegner Lysholm, Tegner Activity Score); demographic and perioperative characteristics; safety

1. Analysis Populations

- **Full Analysis Set (FAS):** All patients who met inclusion criteria, underwent ACL reconstruction with BPTB autograft, were assigned to one of the two cohorts (Vivostat vs. Standard) and had at least one postoperative follow-up assessment. All efficacy analyses (sensory deficit and subjective scores) will be based on the FAS.
- **Safety Set:** All operated patients for whom group assignment (Vivostat vs. Standard) is known. Safety (complications, adverse events) will be summarized descriptively in this set.

No separate per-protocol analysis is planned because all 53 included patients completed follow-up according to the study results.

2. Endpoints

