2.1 Primary endpoint

The **primary endpoint** is the **presence of sensory deficit at the donor site** at postoperative follow-ups:

- Sensory deficit is assessed in a predefined skin area lateral to the incision and coded as a binary variable:
 - **0 = no sensory deficit** (normal perception in all points);
 - **1 = sensory deficit present** (numbness or altered sensation in more than three tested points).

Measurements are performed at:

Study Protocol Title: Impact of Platelet-Rich Fibrin on Donor Site Regeneration and Functional Recovery after ACL Reconstruction with BPTB Autograft

Version 01, 21 September 2020

- 4 months after surgery,
- 8 months after surgery,
- 12 months after surgery.

The primary focus of the analysis is:

1. **Between-group comparison** (Vivostat vs. Standard) of the proportion of patients with sensory deficit (0/1) at each time point, with special emphasis on the 12-month result.
2. **Within-group change over time** (4 vs. 8 vs. 12 months) in the proportion of patients with sensory deficit.

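### The SAP dated 21 September 2020 was written or edited after the 12-month results were known, and it departs from the protocol's outcomes without saying so

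*SAP*

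**What the plan says.** **Date and software.** The SAP cover and page headers read "Version 01, 21 September 2020". SAP section 3 names R "version 4.3.1 (2023-06-16").

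**Results in the plan.**
- SAP section 1 omits a per-protocol analysis because "all 53 included patients completed follow-up according to the study results". Section 8 repeats that follow-up was complete.
- Section 5 says of the Tegner Activity Score that "in the current dataset, no statistically significant change over time was observed".
- Section 6.1 gives significance by visit: p < 0.05 at 8 months, p < 0.01 at 12 months, none at 4 months.
- Section 6.2 says when recovery in the PRF group mainly took place.
- Section 7 gives 12-month proportions without deficit of 79% and 34%, with power 0.93.

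**Primary endpoint.** Protocol section 6 sets it at 12 months only. The SAP cover has "Sensory deficit at the donor site over time (4, 8 and 12 months"). SAP section 2.1 lists two primary analyses: the groups compared at each visit, "with special emphasis on the 12-month result", and change over time within each group.

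**Secondary outcomes.** Protocol section 6 lists four: MRI healing, functional scores, satisfaction and adverse events. The SAP covers scores and safety and adds baseline characteristics. It mentions neither MRI nor satisfaction.

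**Multiplicity.** SAP section 3 promises Bonferroni correction "For multiple pairwise comparisons of the same endpoint (e.g., sensory deficit across the three follow-up time points"). Section 6.2 applies it to the three McNemar tests. Section 6.1 mentions no correction.

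**The concern.** A plan with a 2020 date and mostly future-tense wording invites the reader to treat its choices as fixed before the data were seen. If the text was written or edited with the results in hand, that reading is wrong. Nothing in either document shows which endpoint, visit or test was settled beforehand.

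This matters more because the SAP and protocol differ on outcomes and the differences are not declared. SAP section 10 promises to document deviations from the SAP, not differences between the SAP and the protocol. MRI healing bears directly on the donor-site regeneration in the study title, yet it has no specified analysis. The stakes are how the findings may be labelled, whether two protocol outcomes will be reported, and whether the 8-month difference may be called significant.

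**Working it through.** **1. Date gap.** From 21 September 2020 (SAP cover) to 21 September 2022 is 730 days. From there to 16 June 2023 (SAP section 3) is 268 days. 730 + 268 = 998 days, about 32.8 months. A text that prints the later date was not completed on the earlier one.

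**2. The SAP's own power figure.** Inputs from SAP section 7: p1 = 0.79, n1 = 24; p2 = 0.34, n2 = 29; two-sided alpha 0.05; pooled z-test.
- Pooled proportion = (24 × 0.79 + 29 × 0.34)/53 = 28.82/53 = 0.544.
- Null SE = √[0.544 × 0.456 × (1/24 + 1/29)] = 0.1374.
- Alternative SE = √[0.79 × 0.21/24 + 0.34 × 0.66/29] = 0.1210.
- Power = Φ[(0.45 − 1.96 × 0.1374)/0.1210] = Φ(1.49) = 0.932.

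The stated 0.93 is reproduced. It is computed from the observed 12-month proportions, so this passage cannot have been written before they were known.

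**3. Does the protocol establish prespecification?** It does not. Although dated 18 September 2020, it is in the past tense, gives final group sizes of 24 and 29 (section 3), and reports a power calculation from the 12-month results (section 9).

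**4. Outcomes side by side.**

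| Item | Protocol | SAP |
|---|---|---|
| Primary time point | 12 months (section 6) | 4, 8 and 12 months, plus within-group change (cover, 2.1) |
| MRI healing | Secondary (section 6) | Not mentioned |
| Satisfaction | Secondary, at 12 months (sections 6, 7) | Not mentioned |
| Functional scores | IKDC, Lysholm | These plus Modified Cincinnati and Tegner Activity |
| Continuous variables | t-tests (section 9) | Wilcoxon tests (sections 3–5) |

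The 4- and 8-month visits were already scheduled in protocol section 7; what is new is their primary status. The last two rows are minor, and the change to Wilcoxon tests is defensible.

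**5. The 12-month result.** 19 is the only count out of 24 that rounds to 79% (18 gives 75.0%, 20 gives 83.3%). 10 is the only count out of 29 that rounds to 34% (9 gives 31.0%, 11 gives 37.9%).
- Difference = 0.7917 − 0.3448 = 0.4468, or 44.7 points.
- Wilson limits are 0.595 to 0.908 and 0.199 to 0.527. Newcombe lower limit = 0.4468 − √[(0.7917 − 0.595)² + (0.527 − 0.3448)²] = 0.179. Upper limit = 0.4468 + √[(0.908 − 0.7917)² + (0.3448 − 0.199)²] = 0.633.
- Chi-squared = 53 × (19 × 19 − 5 × 10)²/(24 × 29 × 29 × 24) = 10.58, p = 0.0011. With continuity correction it is 8.86, p = 0.0029. Fisher p = 0.0020.
- Multiplied by 3: 0.0034, 0.0088 and 0.0061. All stay below 0.05.

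**6. The 8-month result.** Only p < 0.05 is given. A corrected threshold would be 0.05/3 = 0.0167. A p-value between 0.0167 and 0.05 satisfies the SAP's statement but not that threshold. No 8-month counts are given for either group, so nothing more can be calculated.

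**The case against.** The strongest reply concerns the primary test. Protocol section 6 fixes 12 months, SAP section 2.1 emphasises it, section 7 refers to the primary endpoint at that visit, and section 6.1 names the chi-squared test with Fisher's as fallback. A 12-month between-group chi-squared test is the natural reading. This stands: what is missing is formal designation, which is a lesser point than the dating.

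Bonferroni in SAP section 3 concerns pairwise comparisons, and section 6.2 implements it, so the between-group tests are most naturally read as uncorrected. That also largely stands; a clarifying sentence is still needed because the example in section 3 is sensory deficit across the three visits.

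The SAP is also open in places: it speaks of observed proportions and study results and never calls its analyses prespecified. That softens the harm but does not correct the date. Section 6.1 words its significance statements as expectations, but the observed figures in section 7 rule out reading the whole text as a forecast.

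The protocol's sentence on chi-square and t-tests might be thought to cover MRI and satisfaction. It assigns them no variable, visit or test.

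Some stronger readings are not supported:
- *The software date proves data access.* It proves only late editing; the result statements show that results were known.
- *No plan existed before the data, or the date was deliberately false.* An earlier version may exist. The available text gives no enrolment dates, so the 2020 date cannot be placed relative to follow-up.
- *MRI and satisfaction were dropped because of their results.* The documents do not show whether they were analysed. Selective reporting can be neither shown nor excluded.
- *The 8-month result would fail correction.* Any assumed counts decide the answer. With 17/24 against an assumed 10/29 the continuity-corrected p is 0.0183; against 9/29 it is 0.0091.

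**Conclusion.** The point holds, and the plan must be corrected. The current SAP text was written or edited after the 12-month results were known, under a label 998 days earlier than the software date it cites. Neither document establishes prespecification. Two of four protocol secondary outcomes have no specified analysis in the SAP, and the primary endpoint was widened, in both cases without declaration. The undesignated primary test is a lesser matter.

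The 12-month difference of 44.7 points (95% CI 17.9 to 63.3) survives the choice of test and a threefold correction. A reader might infer that it is robust in general, but the check does not reach that far. SAP section 2.1 codes 0 as normal at all points and 1 as more than three altered points, leaving one to three altered points without a code. The comparison is also non-randomized and unadjusted.

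The calculation assumes counts of 19/24 and 10/29, the only ones that fit the stated percentages and group sizes. The dating conclusion rests only on the documents' text. The study calls itself a pilot, so what changes is mainly how its findings are labelled and which outcomes are reported.

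**What to change.** - Give the true SAP date and a version history, with any version that predates data access.
- State visibly that the current text post-dates the 12-month results. Deleting the result statements alone would hide the problem.
- Name the 12-month between-group comparison of sensory deficit as the single primary analysis, in line with protocol section 6, with a difference and 95% CI. Do not call it prespecified unless a pre-data version is produced.
- Label the 4- and 8-month between-group comparisons and the within-group tests as secondary or exploratory. Say in section 6.1 whether Bonferroni applies there, and report exact 8-month counts and p-value.
- List the differences from the protocol, including the added scores and the change of test.
- Report MRI healing and satisfaction by group with an estimate and 95% CI, or state why they were dropped.

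The cost is rewording, a version history, a short list of differences and, if the data are available, two group comparisons. The downside is that, without a pre-data version, conclusions (including the 12-month one) must be worded as exploratory, and the 8-month difference may lose its significant label.

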## 2. Objectives

Primary Objective: To evaluate the effect of PRF application on sensory disturbances at the donor site 12 months after ACL reconstruction.

Secondary Objectives: To assess MRI healing of the donor site, functional outcome scores (IKDC, Lysholm), patient satisfaction, and adverse events.

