## 3. Study Design

This is a single-center, prospective, cohort pilot study. Fifty-three patients undergoing ACL reconstruction with BPTB autograft were included. Patients were divided into two groups: Group 1 (PRF group, n=24) with PRF applied at the donor site, and Group 2 (Control group, n=29) with standard closure without PRF. Patients were followed for 12 months postoperatively.

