## 9. Statistical Analysis

Descriptive statistics were used to summarize baseline characteristics. Chi-square test and t-tests were used to compare categorical and continuous variables between groups. A post-hoc power calculation for the primary endpoint was performed based on the 12-month results. All analyses were conducted using standard statistical software.

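### Non-randomised cohort, unadjusted comparisons throughout: the 12-month score comparisons ignore the baseline score already collected, so the PRF comparisons can be biased

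*SAP*

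**What the plan says.** Protocol section 2 sets a causal aim: "To evaluate the effect of PRF application on sensory disturbances at the donor site 12 months after ACL reconstruction". On how the groups arose, protocol section 3 says only "Patients were divided into two groups", and SAP section 1 that patients "were assigned to one of the two cohorts". No allocation rule is given. SAP section 4 states that the cohort is not randomised and gives the baseline tests their purpose: they "serve to document the similarity of groups at baseline in this non-randomized cohort". The variables tested are "age, BMI, time from injury to surgery, length of hospitalization".

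The between-group methods are:

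- Protocol section 9: "Chi-square test and t-tests were used to compare categorical and continuous variables between groups".
- SAP section 5: Wilcoxon rank-sum on each score at baseline and, separately, at 12 months. Change is tested only within each group.
- SAP section 6.1: chi-squared or Fisher's exact test for sensory deficit at 4, 8 and 12 months, tabulated as frequencies, percentages and p-values.
- SAP section 9: a graph and Spearman correlations, both exploratory.

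No regression, ANCOVA, stratification, propensity method or between-group test of change appears. Yet SAP section 2.2 says of the four functional scores: "Each is measured preoperatively (baseline) and at 12 months postoperatively".

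**The concern.** Without randomisation, any prognostic difference between the groups enters the crude comparison. The only safeguard offered is a set of baseline significance tests, and at this sample size a non-significant result says little about similarity.

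The functional scores are the clearest case. A preoperative gap carries over to 12 months in proportion to the correlation between the two measurements. Testing baseline in one analysis and 12 months in another does not correct for that, nor do separate within-group tests of change. Since section 5 promises only p-values for the scores, what is at risk there is the validity of the test.

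For sensory deficit no preoperative value is listed, so adjustment would have to rest on other covariates. What is at risk there is the size of the difference that this pilot reports.

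**Working it through.** **Inputs from the documents.** Group sizes 24 and 29; 79% and 34% without deficit at 12 months (SAP section 7), which implies 19/24 and 10/29. **Assumptions**, because the documents give no values: baseline imbalance, strength of confounder, baseline-to-12-month correlation, reliability of the baseline score.

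**1. The plan's own figure.** Pooled proportion (24×0.79 + 29×0.34)/53 = 0.544. Pooled SE 0.1374, unpooled SE 0.1210. Power = Φ[(0.45 − 1.96×0.1374)/0.1210] = Φ(1.49) = 0.932. The stated 0.93 reproduces. It concerns random error only and says nothing about confounding.

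**2. What the baseline tests can detect.** Simulated power of the Wilcoxon test, 24 vs 29, normal data:

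| True imbalance (SD) | 0.2 | 0.3 | 0.5 | 0.8 |
|---|---|---|---|---|
| Detected | 10% | 18% | 41% | 79% |

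A 0.5 SD imbalance is missed about 59% of the time.

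**3. Functional scores.** Bias of the crude 12-month difference = correlation × baseline gap. At a 0.5 SD gap: 0.3×0.5 = 0.15, 0.5×0.5 = 0.25, 0.7×0.5 = 0.35 SD. Rejection rate of the planned 12-month Wilcoxon test when there is no true effect (nominal 5%):

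| Gap (SD) | r = 0.3 | r = 0.5 | r = 0.7 |
|---|---|---|---|
| 0.3 | 5.7% | 8.2% | 11.0% |
| 0.5 | 8.2% | 13.4% | 22.2% |

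**4. What baseline adjustment leaves.** If the groups differ only through an error-free baseline score, ANCOVA bias is at most 0.004 SD. That is a favourable case. If the gap lies in the true score and the baseline is measured with reliability R, ANCOVA leaves correlation × gap × (1/R − 1). With a 0.5 SD gap and r = 0.5 / 0.7:

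- R = 0.8: 0.25×0.25 = 0.06 and 0.35×0.25 = 0.09 SD.
- R = 0.7: 0.25×0.429 = 0.11 and 0.35×0.429 = 0.15 SD.

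The corresponding crude biases (correlation × gap / R) are 0.31 and 0.44 SD, and 0.36 and 0.50 SD. Adjustment removes most of the bias from the measured baseline difference, not all of it.

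Precision: the variance of the adjusted difference, relative to the crude one, is (1 − r²)[1 + (1 + gap²/(1/24 + 1/29))/49]. At r = 0.3 / 0.5 / 0.7 the cut is 7 / 23 / 48% with no gap and 1 / 18 / 45% at 0.5 SD. At low correlation the gain is in bias, not precision.

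**5. Sensory deficit at 12 months.** Crude risk difference 19/24 − 10/29 = 0.792 − 0.345 = 0.447 (Newcombe 95% CI 0.179 to 0.633). Risk ratio 2.30 (1.34 to 3.95). E-value = 2.296 + √(2.296×1.296) = 4.0; for the lower limit, 1.335 + √(1.335×0.335) = 2.0.

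Shift in risk difference, in points, from a normal confounder with no true effect and 29/53 overall without deficit:

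| Imbalance (SD) | OR 1.5 per SD | OR 2 | OR 3 |
|---|---|---|---|
| 0.2 | 1.9 | 3.1 | 4.4 |
| 0.3 | 2.9 | 4.6 | 6.5 |
| 0.5 | 4.8 | 7.7 | 10.9 |

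Across this grid, 0.1 to 0.7% of confounding-only simulations reach 44.7 points.

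A binary confounder gives a bias factor [1 + (RRc − 1)p₁]/[1 + (RRc − 1)p₀], where RRc is its risk ratio for no deficit and p₁, p₀ its prevalence in the PRF and control groups. With RRc 1.5 to 3 and prevalence 60/40 to 80/20, the factor runs from 1.08 to 1.86, so the risk ratio falls from 2.30 to between 2.12 and 1.24 if confounding favours PRF, and rises if it favours control. The lower limit drops below 1 only when the factor exceeds 1.34.

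**6. Choice of adjusted estimator.** Simulated risk differences in points, 24 vs 29, group plus three covariates:

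| Scenario | True | Crude | Firth | Logistic, standardised | Linear |
|---|---|---|---|---|---|
| No confounding | 44.5 | – | 41.2 | 44.4 | 44.7 |
| OR 2, 0.5 SD | 44.3 | 50.6 | 41.3 | 44.1 | 44.7 |

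Ordinary logistic regression failed in at most 1.3% of runs; the linear model cannot fail through separation.

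**The case against.** Restriction already controls some confounding. Protocol section 4 limits age to 18–40 and excludes previous surgery on the knee, additional ligament reconstruction, severe cartilage damage and interfering systemic disease; the SAP reports an all-male sample. This stands as mitigation, but it does not balance the groups within those limits.

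The SAP already calls the baseline tests descriptive. True, so rewording their purpose is a small matter. The missing adjustment and the missing allocation rule are not.

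SAP section 3 justifies rank tests: "Because most continuous variables deviate from normality or sample sizes are modest". That does not rule out adjustment. In simulations with left-skewed scores, or with 30% of 12-month values at the ceiling, ANCOVA bias was at most 0.005 SD and coverage 94.9 to 95.4%. A proportional-odds model serves an ordinal score.

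Any adjusted analysis is now post hoc, and this applies to the scores as much as to sensory deficit: follow-up is complete, and SAP section 5 already reports a Tegner Activity result. This stands in full. So does the point that nothing shows age, BMI or time from injury to surgery to be the confounders. In simulation, when the confounder was left out of the adjusted (Firth) model, over 90% of the bias remained in most settings.

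A reader might infer that the 12-month sensory difference is an artefact of group selection. The documents do not support that: they show no imbalance, and confounding of the size examined rarely produces a difference this large. A reader might equally infer that adjusting for baseline makes the score comparison unbiased. It does not, as step 4 shows, and unmeasured confounding from the unexplained allocation is untouched.

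**Conclusion.** The concern holds in this form: the cohort is non-randomised with no stated allocation rule, every between-group comparison is unadjusted, and baseline scores in hand are left out of the 12-month comparison. The comparisons can be biased; whether they are, and in which direction, cannot be told from the documents.

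The case for adjustment is strongest for the functional scores, which are secondary: 0.15 to 0.35 SD of crude bias and about 8 to 22% false rejection, conditional on an assumed 0.5 SD gap and correlation 0.3 to 0.7. Smaller gaps give proportionately less bias. Adjustment reduces this, with about 0.06 to 0.15 SD remaining at reliability 0.7 to 0.8 and correlation 0.5 to 0.7.

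For sensory deficit, adjustment is a supporting sensitivity analysis. A shift of roughly 2 to 11 points under the continuous-confounder assumptions bears on the size of the 44.7-point difference and is unlikely to account for all of it.

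**What to change.** **Main (SAP section 5).** Add a between-group comparison of each 12-month score adjusted for the baseline score of the same instrument: ANCOVA, or a proportional-odds model for skewed scores and the Tegner Activity Score. Report the adjusted difference or odds ratio with 95% CI beside the planned Wilcoxon tests, labelled post hoc.

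**Supporting (SAP section 6.1).** Keep chi-squared/Fisher as the main result. Add one sensitivity analysis, also labelled post hoc: an adjusted 12-month risk difference with 95% CI, from ordinary logistic standardisation or a linear model with robust standard errors, on group, age, BMI and time from injury to surgery. Fix the covariates before running it. Leave out length of hospitalisation, which follows surgery. Avoid Firth standardisation, which shrinks a difference of 44 to 46 points by 3 to 4 points.

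**Text.** State how patients came to each group, since adjustment cannot repair an unknown allocation process. Describe the baseline data without claiming that tests show similarity. Present the PRF result as an association that may be confounded. Record the additions under SAP section 10.

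**Cost.** SAP wording and a few lines of R on data already collected; the score adjustment uses one degree of freedom for ANCOVA. The adjusted analyses are post hoc, the adjusted risk-difference interval is usually somewhat wider, and unmeasured confounding remains.
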